8.1.1 Baseline Characteristics

All baseline summary statistics will be based on characteristics prior to the initiation of study drug. Unless otherwise stated, baseline for a given variable will be defined as the last value for that variable obtained prior to the first dose of study drug.

8.1.1.1 Demographics

Descriptive statistics will be provided for baseline demographic variables. Age, height and weight will be summarized with means, medians, standard deviations and ranges. Frequencies and percentages will be provided for gender and race.

8.1.1.2 Medical Histories

Frequencies and percentages will be summarized for each medical history parameter.

8.1.2 Study Endpoints

8.1.2.1 Primary Endpoint

The primary endpoint will be assessed by the GHS/QoL subscale of the EORTC QLQ-C30. The primary endpoint will be the mean change from baseline (within 72 hours prior to the first dose of venetoclax) to Week 48. Scores will be calculated based on the scoring manual.

8.1.2.2 Secondary Endpoints

Secondary quality of life endpoints will include all multi-item scales and single-item scales from the EORTC QLQ-C30, EORTC QLQ-CLL16, and EQ-5D-5L. Scores will be calculated based on the scoring manual for each instrument.

Key secondary efficacy endpoints will include Complete Remission rate (CR + CRi), Overall Response Rate (ORR), Duration of Overall Response (DOR), Time to Progression (TTP), Duration of Progression-Free Survival (PFS) and Overall Survival (OS).

Complete remission rate (CR + CRi) defined as the proportion of subjects achieving a CR or CRi as their best response (per the investigator assessment) based on IWCLL NCI-WG criteria. In addition, the ninety-five percent (95%) confidence interval based on binomial distribution will be constructed for the calculated CR rate.

ORR will be assessed as the proportion of subjects with an overall response (CR + CRi + nPR + PR) based on the IWCLL NCI-WG criteria. The ninety-five percent (95%) confidence interval based on binomial distribution will be constructed for the calculated CR rate.

Duration of overall response will be defined as the number of days from the date of first response (CR, CRi, nPR, or PR) to the earliest recurrence or PD. If a subject is still responding, then the subject's data will be censored at the date of the subject's last available disease assessment. For subjects who never experience response, the subject's data will be censored on the date of enrollment. Duration of overall response will be analyzed by Kaplan-Meier methodology using data for all enrolled subjects. Median duration of overall response will be calculated and the corresponding 95% confidence interval will be presented.

Time to progression (TTP) will be defined as the number of days from the date of first dose or enrollment if not dosed to the date of earliest disease progression. All disease progression will be included regardless whether the event occurred while the subject was taking the study drug or had previously discontinued the study drug. If the subject does not experience disease progression, then the data will be censored at the date of last available disease assessment. Data for subjects who receive non-protocol, CLL therapy prior to disease progression will be censored at the last disease assessment prior to receiving non-protocol therapy. Data for subjects without any disease assessments performed after the baseline visit will be censored at the time of enrollment plus 1 day. TTP will be analyzed by Kaplan-Meier methodology using data for all subjects enrolled. Median time TTP will be calculated and 95% confidence interval for median time TTP will be presented.

Progression-free survival (PFS) will be defined as the number of days from the date of first dose to the date of earliest disease progression or death. All disease progression will be included regardless whether the event occurred while the subject was taking the study drug or had previously discontinued the study drug. If the subject does not experience disease progression or death, then the data will be censored at the date of last disease

assessment. Data for subjects who receive non-protocol, CLL therapy prior to disease progression will be censored at the last disease assessment prior to receiving non-protocol therapy. Data for subjects without any disease assessments performed after the baseline visit will be censored at the time of enrollment plus 1 day. PFS will be analyzed by Kaplan-Meier methodology using data for all subjects enrolled. Median time PFS will be calculated and 95% confidence interval for median time PFS will be presented.

Overall survival (OS) will be defined as number of days from the date of first dose to the date of death for all dosed subjects. For subjects who did not die, their data will be censored at the date of last study visit or the last known date to be alive, whichever is later. OS will be analyzed by Kaplan-Meier methodology using data from all enrolled subjects. Median time survival will be estimated and 95% confidence interval for the median time survival will be presented.

8.1.3 Timing of Study Endpoints and Safety Evaluations

The date the last enrolled subject has completed their Week 48 quality of life and disease assessments, or after all enrolled subjects have discontinued venetoclax, whichever is earlier, will be defined as the data "cutoff" date for the analyses. Quality of life, efficacy and safety data up to and including this date will be collected. Exact data cutoff date for the analysis will be detailed in the SAP which will be signed off prior to the data cut-off date. During this data collection period, active subjects will continue to receive venetoclax, as applicable. When data collection is complete and all data management quality assurance (QA) and quality control (QC) procedures are performed, the clinical database data will be extracted for documentation and statistical analyses. Any active subjects will continue to receive venetoclax until they discontinue or for up to 2 years. Once the last enrolled subject discontinues/completes the study, the study will be considered complete and all remaining data will be collected and entered into the clinical database.

8.1.4 Safety

The safety of venetoclax will be assessed by evaluating study drug exposure, adverse events, serious adverse events, all deaths, and laboratory parameters.

Safety analyses will be performed for all subjects who take at least one dose of venetoclax.

8.1.4.1 Adverse Events

Analyses of adverse events will include only "treatment-emergent" events, i.e., those that have an onset on or after the day of the first dose of study drug.

Analyses will not include those that have an onset greater than 30 days after the last dose of study drug.

Treatment-emergent adverse events will be summarized by preferred terms within a System and Organ Class according to the most current Medical Dictionary for Regulatory Activities (MedDRA). In addition, the percentage of subjects experiencing an adverse event at a NCI CTCAE toxicity grade, and relationship to study drug will be provided.

8.1.4.2 Serious Adverse Events

Serious adverse events will be summarized using the same methods as Adverse Events described above.

8.1.4.3 Deaths

The number of subject deaths will be summarized (1) for deaths occurring within 30 days of the last dose of study drug, and (2) for deaths occurring more than 30 days of the last dose of study drug.

8.1.4.4 Analyses of Laboratory Data

Where applicable, blood chemistry and hematology determinations will be categorized according to NCI CTCAE version 4.03, grades and shifts from baseline NCI CTCAE grades to maximum and final post-baseline grades will be assessed.

The baseline and final grades will be defined respectively as the grade of the last measurement collected prior to the first dose of study drug, and as the last post-baseline measurement collected no more than 30 days after the last dose of study drug. The percentage of subjects experiencing a shift from baseline grades of 0 to 2 to maximum post-baseline grades of 3 to 4, and from baseline grades of 0 to 2 to final post-baseline grades of 3 to 4 will be summarized. Detailed listings of data for subjects experiencing NCI CTCAE Grade 3 to 4 blood chemistry and hematology values will be provided. All measurements collected, regardless of the number of days after the last dose of study drug, will be included in these listings.

8.2 Determination of Sample Size

An improvement in the EORTC QLQ-C30 GHS/QoL subscale of 5 units is considered to be a clinically meaningful difference to subjects. From a prior study of venetoclax monotherapy in 17p del R/R CLL subjects (Study M13-982), the standard deviation was approximately 20.5 for the GHS/QoL subscale. Using a one-sided alpha of 0.025, 90% power, and a standard deviation of 20.5; 177 subjects are required to reject the null hypothesis in favor of the alternative hypothesis that venetoclax improves GHS/QoL by at least 5 units. To account for potential drop-outs at Week 48, a total of 200 subjects to be dosed.

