Duration of Treatment:	
Subjects may continue receiving venetoclax for up to 2 years provided they continue to tolerate the drug, have no evidence of disease progression (based on investigator assessment), do not have unacceptable toxicity, and do not meet any of the criteria for subject discontinuation. After treatment discontinuation, subjects will be followed for disease progression (if progression has not already occurred) and survival. Post-treatment calls will be performed every 6 months until discontinuation from the study. Survival information (i.e., the date and cause of death, post-treatment cancer therapies, date of progression etc.) will be collected. This period will continue for 2 years following discontinuation of venetoclax.
 
In countries where venetoclax is not commercially available, subjects who continue to derive benefit after 2 years of treatment, may be able to extend their treatment for up to 2 additional years. AbbVie will work with the investigator on a case by case basis to consider the potential continuation of venetoclax therapy.

Criteria for Evaluation:	
Quality of Life: Quality of life will be assessed based on patient-reported outcome (PRO) measures, including the EORTC QLQ-C30, EORTC QLQ-CLL16, and EQ-5D-5L.
 
Efficacy: Disease response will be assessed by the investigator, based on laboratory results, physical examinations, using the 2008 modified IWCLL NCI-WG Criteria for Tumor Response including CT imaging (or MRI in the case CT is medically contraindicated) and bone marrow biopsy and aspirate for subjects with CR to confirm the response.
 
All measurable disease must be documented at Screening (baseline) by physical examination, laboratory testing, and CT scan (or MRI in the case CT is medically contraindicated). During the study, clinical disease assessments will take place at Week 24, Week 36, and Week 48. To confirm the response, a CT scan will be performed at Week 48.
 
Safety: Adverse event monitoring, vital signs, physical examination, and laboratory assessments will be evaluated.

Statistical Methods:

The study analyses will be descriptive. All subjects participating in the study who received at least one dose of venetoclax will be included in the analyses unless otherwise noted in the separate, statistical analysis plan (SAP).

Study Variables:

Quality of Life:

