5.3.2.2.1 Quality of Life Assessments

EORTC QLQ-C30

Quality of life and symptoms will be assessed with the European Organization for Research and Treatment of Cancer (EORTC) Quality of Life Questionnaire Core 30 (EORTC-QLQ-C30) version 3.³⁶ The QLQ-C30 is a 30-item subject self-report questionnaire composed of both multi-item and single scales, including five functional scales (physical, role, emotional, social, and cognitive), three symptom scales (fatigue, nausea and vomiting, and pain), a global health status/quality of life (GHS/QoL) scale, and six single items (dyspnea, insomnia, appetite loss, constipation, diarrhea, and financial difficulties). Subjects rate items on a four-point scale, with 1 as "not at all" and 4 as "very much." The EORTC QLQ-C30 was developed and validated for use in a cancer subject population, and its reliability and validity is highly consistent across different language cultural groups. A change of 5 – 10 points is considered a small change, and the lower bound (5) is being used to define the minimum important difference (MID). A change of 10 – 20 points is considered a moderate change.

EORTC QLQ-CLL16

The EORTC QLQ-CLL16 was designed specifically for subjects with stage 0 to stage 4 CLL.³⁷ It is comprised of sixteen questions that address five domains of HRQoL important in CLL. There are three multi-item scales assessing Fatigue (2 items), Disease and Treatment Effects (7 items), and Infection (5 items), and two single-item scales assessing Social Activities and Future Health Worries. Subjects rate items on a four-point scale, with 1 as "not at all" and 4 as "very much." A negative change in score from baseline represents an improvement in symptoms. A change of 5 – 10 points is considered a small change, and the lower bound (5) is being used to define the minimum important difference (MID). A change of 10 – 20 points is considered a moderate change.³⁸⁻⁴⁰

EQ-5D-5L

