9.0 Ethics

9.1 Independent Ethics Committee (IEC) or Institutional Review Board (IRB)

Good Clinical Practice (GCP) requires that the clinical protocol, any protocol amendments, the Investigator's Brochure, the informed consent and all other forms of

subject information related to the study (e.g., advertisements used to recruit subjects) and any other necessary documents be reviewed by an IEC/IRB. The IEC/IRB will review the ethical, scientific and medical appropriateness of the study before it is conducted. IEC/IRB approval of the protocol, informed consent and subject information and/or advertising, as relevant, will be obtained prior to the authorization of drug shipment to a study site.

Any amendments to the protocol will require IEC/IRB approval and approval by Regulatory Authority(ies), if required by local regulations, prior to implementation of any changes made to the study design. The investigator will be required to submit, maintain and archive study essential documents according to ICH GCP and all other applicable regulatory requirements.

Any serious adverse events that meet the reporting criteria, as dictated by local regulations, will be reported to both responsible Ethics Committees and Regulatory Agencies, as required by local regulations. During the conduct of the study, the investigator should promptly provide written reports (e.g., ICH Expedited Reports, and any additional reports required by local regulations) to the IEC/IRB of any changes that affect the conduct of the study and/or increase the risk to subjects. Written documentation of the submission to the IEC/IRB should also be provided to AbbVie.

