10.1.1 Definitions for Quality of Life Assessments

EORTC QLQ-C30

Quality of life and symptoms will be assessed with the European Organization for Research and Treatment of Cancer (EORTC) Quality of Life Questionnaire Core 30 (EORTC-QLQ-C30) version 3¹. The QLQ-C30 is a 30-item subject self-report questionnaire composed of both multi-item and single scales, including five functional scales (physical, role, emotional, social, and cognitive), three symptom scales (fatigue, nausea and vomiting, and pain), a global health status/quality of life (GHS/QoL) scale, and six single items (dyspnea, insomnia, appetite loss, constipation, diarrhea, and financial difficulties). Subjects rate items on a four-point scale, with 1 as "not at all" and 4 as "very much." The EORTC QLQ-C30 was developed and validated for use in a cancer subject population, and its reliability and validity is highly consistent across different language cultural groups. A change of 5 – 10 points is considered a small change, and the lower bound (5) is being used to define the minimum important difference (MID). A change of 10 – 20 points is considered a moderate change.

The EORTC-QLQ-C30 domains (global health status/quality of life, physical, role, emotional, social, cognitive, fatigue, nausea and vomiting, pain, dyspnoea, insomnia, appetite loss, constipation, diarrhea, and financial difficulties) will be summarized (mean, standard deviation, and median) at each assessment. In addition the mean change in each of these values (visit-level assessment versus baseline) will be calculated to identify any statistically significant differences. The ninety-five percent (95%) confidence interval of the mean change will be constructed based on (a) without model assumption and (b) with model assumption. A linear model will be used for the analysis of repeated measures where the covariance pattern will be assumed as compound symmetry (CS).

EORTC QLQ-CLL16

The EORTC QLQ-CLL16 was designed specifically for subjects with stage 0 to stage 4 CLL². It is comprised of sixteen questions that address five domains of HRQoL important in CLL. There are three multi-item scales assessing Fatigue (2 items), Disease

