10.2.1 Primary Endpoint Analysis

The primary endpoint will be assessed by the GHS/QoL subscale of the EORTC QLQ-C30. Summary stats will be on mean change. The endpoint (at subject level) will be mean change from baseline to Week 48. Scores will be calculated based on the scoring manual. Mean score for baseline visit and post-baseline visit (Week 4, Week 12, Week 24, Week 36, Week 48, Week 60, Week 72, Week 84, Week 96, and Week 108/Final visit) will be reported with standard deviation (SD). The 95% confidence interval for mean change additionally will be provided for each post-baseline versus baseline.

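### The sample-size statement claims a test for a gain of at least 5 units, but 177 subjects is the number for a test against no change

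*Protocol*

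**What the plan says.** The same sample-size sentence stands in Protocol 8.2, the Protocol synopsis (Sample Size Estimation) and SAP 4.3: "177 subjects are required to reject the null hypothesis in favor of the alternative hypothesis that venetoclax improves GHS/QoL by at least 5 units". The inputs are one-sided alpha 0.025, 90% power and an SD from Study M13-982, where "the standard deviation was approximately 20.5 for the GHS/QoL subscale". Five units is called clinically meaningful there, and Protocol 5.3.2.2.1 and SAP 10.1.1 both adopt 5 as the MID for the QLQ-C30. None of the three paragraphs states a null value or an assumed true change other than 5.

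On analysis, the synopsis says "The study analyses will be descriptive". SAP 10.1.1 says that "the mean change in each of these values (visit-level assessment versus baseline) will be calculated to identify any statistically significant differences". SAP 10.2.1 plans the mean change from baseline to Week 48 and adds: "The 95% confidence interval for mean change additionally will be provided for each post-baseline versus baseline". It sets no success criterion and does not say whether the interval is to be read against 0 or against 5.

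**The concern.** In a power calculation, the effect size is the true value at which the stated power holds. It is not what rejection proves; rejection excludes only the null. The sentence here turns the planning effect into the alternative that rejection is said to establish.

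That matters because 5 is the plan's own threshold for an important change on the primary endpoint. Taken at its word, the sentence would let a result that is significant against zero be reported as a mean gain of at least the MID. The planned comparison cannot show that by itself.

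**Working it through.** **Inputs.** SD 20.5, one-sided alpha 0.025, power 90% and effect 5 (Protocol 8.2). Single arm (Protocol 5.6.1) and mean change from baseline to Week 48 (Protocol 8.1.2.1), so a one-sample problem. 20.5 is taken as the SD of the change, which the documents do not say.

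**Reproducing 177.** With null 0 and true change 5:

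n = ((z₀.₉₇₅ + z₀.₉₀) × SD / 5)² = ((1.95996 + 1.28155) × 20.5 / 5)² = 176.63, rounded up to 177.

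Power at n = 177 is 90.1% by the normal approximation and 89.7% by the t-test.

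**Testing the alternative as worded.** If the null were a mean change of 5 or less, a true change of 5 would lie on its boundary and be rejected 2.5% of the time at any n. The n for 90% power would depend on a larger true change, which the documents do not give. With n = ((1.95996 + 1.28155) × 20.5 / (true change − 5))²:

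| Assumed true change | n for 90% power against a null of 5 | Power at n = 177 (t-test) |
|---|---|---|
| 6 | 4416 | 9% |
| 7 | 1104 | 25% |
| 8 | 491 | 49% |
| 9 | 276 | 73% |
| 10 | 177 | 90% |

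The figure 177 returns only at a true change of 10, because the distance from the null is again 5. No section assumes a change of 10.

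**What the planned interval can show.** A two-sided 95% CI lying above 0 corresponds to the one-sided 0.025 test. For the simple interval at n = 177:

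- Standard error = 20.5 / √177 = 1.541.
- Half-width = t₀.₉₇₅,₁₇₆ × 1.541 = 3.04.
- The interval excludes 0 once the observed mean change exceeds about 3.04.
- An observed mean of 5 gives 5 ± 3.04, or 1.96 to 8.04.
- For the interval to lie wholly above 5, the observed mean must exceed about 5 + 3.04 = 8.04.

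The chance of significance against 0 at n = 177 (t-test) is 9%, 25%, 49% and 73% at true changes of 1, 2, 3 and 4. If all 200 subjects were evaluable, the half-width would be 2.86 and the chance at a true change of 4 would be 78%.

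**Sensitivity to the SD.** If 20.5 is instead the SD at a single visit, equal at both visits, the SD of the change is 20.5 × √(2(1 − ρ)), where ρ is the baseline to Week 48 correlation. The documents give no ρ. For an assumed range:

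| ρ | SD of change | Half-width, n = 177 | Power against 0 at a true change of 5 |
|---|---|---|---|
| 0.3 | 24.3 | 3.60 | about 78% |
| 0.5 | 20.5 | 3.04 | about 90% |
| 0.7 | 15.9 | 2.36 | about 99% |

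The size of the gap changes with ρ. In every row an observed mean below 5 can still be significant against 0.

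**The case against.** The strongest reply is that a sample-size sentence may name as its alternative the values the study is powered to detect. With a null of 0, power is about 90% at a true change of 5 and higher above it, so the sentence could be read as loose rather than wrong. But it speaks of rejecting in favour of that alternative, which is a claim about what rejection supports. A charitable reader can supply the other meaning; the text does not.

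It is fair to say that the null of 0 is inferred. It rests on the arithmetic, on 5 being the only effect size given, and on SAP 10.1.1 judging significance against baseline.

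It is also fair that the harm is one of interpretation. The analyses are called descriptive, no success rule exists, no section says that significance will be reported as a gain of at least the MID, and a published CI lets the reader make the comparison with 5. That limits the consequence but does not remove it. The plan still states an alpha, a power and a rejection, and it still looks for statistical significance. The sample-size sentence is the only place that ties that inference to 5 units.

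The point about the SD stands as a condition: the figures, and the adequacy of 177, depend on 20.5 being the SD of the change.

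**Conclusion.** The concern holds. The stated alternative is wrong as written in all three places, and nothing in SAP 10.2.1 corrects it. The number 177 is correct for a test against zero change, and the planned mean with CI suits that test, so the defect lies in the claim and not in the design. At the planned n, significance begins about 2 units below the MID (5 − 3.04 = 1.96).

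This rests on a null of 0 and on 20.5 being the SD of the change. The figures are for the simple interval; the repeated-measures interval also planned in SAP 10.1.1 may differ in width. The point should be fixed, because the error concerns what the primary endpoint can be said to show.

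**What to change.** 1. First confirm from the M13-982 data that 20.5 is the SD of the change from baseline. If it is not, power has to be recomputed before the sentence is rewritten.
2. In Protocol 8.2, the synopsis and SAP 4.3, replace the sentence with: *With an SD of 20.5 for the change from baseline and one-sided alpha 0.025, 177 evaluable subjects give about 90% power to reject H0: mean change of 0 or less, in favour of H1: mean change above 0, if the true mean change is 5 units.*
3. In SAP 10.2.1 add: *A 95% CI that excludes 0 does not by itself establish a mean improvement of 5 units or more. The Week 48 mean change and its CI will be read against the 5-unit MID.*
4. As a side item, name which interval this reading uses, since SAP 10.1.1 provides for two: "confidence interval of the mean change will be constructed based on (a) without model assumption and (b) with model assumption". Interval (a) matches the one-sample calculation behind 177.

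No success criterion is needed. If the sponsor does want to show a gain above 5, a larger true change must be justified and the sample size recalculated.

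The cost is one sentence in three places and a short addition. For the protocol text, "Any amendments to the protocol will require IEC/IRB approval", so it can go with the next amendment. SAP 3.0 does not provide for updates after minor protocol amendments unless they affect the analysis, so the SAP text needs its own revision. Provided step 1 confirms the SD, the sample size, data collection and planned summaries stay as they are. The only loss is a less favourable stated claim.
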